|  | 
[REDACTED]
 
The duration of the DPC period for each patient will be 36 weeks. The octreotide capsule dose/placebo should be titrated up per Investigator's discretion, based on significantly increased IGF-1 levels compared to Baseline (average of the 2 assessments within 2 weeks prior to randomization), worsening of acromegaly signs/symptoms or both.
 
The Sponsor recommends any one of the following guiding rules for dose escalation:
 
 
• Significantly increased IGF-1 levels compared to Baseline defined as IGF-1 increase by at least 30% to <math>>1 \times \text{ULN}</math> (this will be flagged by the central laboratory).
 
• IGF-1 levels <math>>1 \times \text{ULN}</math> for 2 consecutive visits.
 
• New or worsening of any one of the following acromegaly signs/symptoms: headache, fatigue, perspiration, soft tissue swelling, arthralgia, dysglycemia or hypertension or other signs that in view of the Investigator are related to acromegaly.
 
 
The dose escalation will be done in a stepwise manner from 1 capsule twice daily; BID (equivalent to 40 mg/day) to 2 capsules in the morning and 1 capsule in the evening/night (equivalent to 60 mg/day) to 2 capsules BID (equivalent to 80 mg/day).
 
The dose can be escalated any time through Week 24 (including Week 24); thereafter the dose must be kept stable. Patients randomized to matching placebo will also undergo mock titrations increasing capsule numbers from 1 capsule twice daily to 2 capsules in the morning and 1 capsule in the evening/night to 2 capsules BID.
 
During the DPC period, patients will return to the clinic for a site visit every four weeks up to week 36 (<math>\pm 5</math> days) and attend an additional in-clinic visit at week 34 (<math>\pm 5</math> days).
 
[REDACTED] Pre-scheduled telephone calls will occur at Weeks 1 and 2. Unscheduled visits will be allowed throughout the study for safety, tolerability or management of active disease, per the Investigator discretion.
 
[REDACTED]
 
All efforts should be made to maintain patients on their randomized arm assignment throughout the DPC period up to completion of the core study.
 
Patients who meet the pre-defined withdrawal criteria [(IGF-1 levels <math>\geq 1.3 \times \text{ULN}</math> AND exacerbation of acromegaly clinical signs or symptoms), for 2 consecutive
 |
|--|---|

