### **2.2 Secondary Objectives**

The following are secondary objectives:

- To assess maintenance of biochemical control, based on GH, with octreotide capsules compared to placebo
- To evaluate the safety profile of octreotide capsules compared to placebo

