## 6 Statistical Methodology

### 6.1 General Methodology

The following is a list of general reporting conventions:

- Percentages will be based on the number of subjects in the analysis set unless otherwise indicated.

- Categorical variables will be summarized using counts (n) and percentages (%) and will be presented in the form of n (%).
- Percentages will be reported to 1 decimal place.
- Continuous data will be summarized using the mean, standard deviation (SD), median, minimum, 25th and 75th percentiles, maximum, and number of subjects with data.
- Means and medians will be reported at 1 more significant digit than the precision of the data. Standard deviations and confidence intervals will be reported at 2 more significant digits than the precision of the data. Quartiles, minima and maxima will be reported to the same level of precision as the original observations.
- The median will be reported as the average of the 2 middle numbers if the dataset contains even numbers.
- No preliminary rounding should be performed; rounding should only occur after analysis. To round, consider digit to right of last significant digit: if  $< 5$ , then round down; if  $\geq 5$ , then round up.
- All p-values will be reported to 3 decimal places (e.g., 0.XXX). Values  $< 0.001$  will be reported as  $< 0.001$ .

If departures from these general conventions are present in the specific evaluations sections of this SAP, then those conventions will take precedence over these general conventions.

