## 6.9 Safety Analyses

All safety analyses for data collected during the DPC period will be presented using the safety set. All safety analyses for data collected during the OLE will be presented using the OLE set (summaries by treatment group will be based on the treatment group in the DPC period). Safety analyses for the DPC period will only use data collected during the DPC period, and will exclude any safety data that was collected after a subject had discontinued study drug. Safety analyses for the OLE will include data collected during the OLE. No formal hypothesis testing will be conducted. Data will be summarized using appropriate descriptive statistics. Missing data will be maintained as missing, unless indicated.

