### 6.9.2.1 DPC period

All AEs that occur after randomization (i.e., date of onset is on or after the date of randomization) and on or before the end of treatment (last dose of blinded study drug) in the DPC period will be considered Treatment Emergent Adverse Events (TEAEs) for the purpose of reporting in the DPC period, and will be summarized using frequency counts and percentages. Summaries will be presented by final dose group and treatment group (i.e., octreotide 40, 60, 80, overall and placebo) and overall for the safety set.

If the day of onset of an AE is missing, then if the month and year of an onset date are on or after the date of randomization, the following rules will be applied:

- If month/year of the onset date is on or after the month/year of randomization, the AE will be considered treatment emergent;
- If month/year of the onset date is equal to the month/year of randomization, and the end date is present, the end date will be used to determine when the AE started. If the end date is on or after randomization, the AE will be considered treatment emergent; otherwise, if the AE stopped before randomization, then it will not be considered treatment emergent;
- If month/year of the onset date is equal to the month/year of randomization, and the end date is a partial date, the AE will be considered treatment emergent;
- If, despite implementing the above conventions, the onset date of the AE cannot be placed before, on, or after randomization, then the event will be considered treatment emergent.

Summaries of TEAEs will be presented using the MedDRA level hierarchy (system organ class, high level group term, high level term, and preferred term) as follows:

- Overall (i.e., regardless of intensity or relationship to treatment)
- By intensity grade (mild, moderate, severe)
- By relationship to study medication (potential relationship to study treatment or unlikely/no relationship to study treatment) according to the mapping scheme below:
  - Related: will include all AEs with a relationship rating of “related” or “possibly related”
  - Not related: will include all AEs with a relationship rating of “Not related”
- Unless otherwise specified, at each level of patient summarization in reporting the incidence of the AEs, a subject will be counted once if the subject reported one or more events. If more than one occurrence of an event is reported, the event of the worst intensity or the worst-case relationship assessment will be summarized.

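### DPC adverse events are compared as crude percentages with counting stopped at last dose, so events spread over the 36 weeks are compared over unequal time at risk if placebo patients stop earlier

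*SAP*

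**What the plan says.** SAP 6.9.2.1 sets the window: adverse events with onset no earlier than randomization that also start "on or before the end of treatment (last dose of blinded study drug) in the DPC period will be considered Treatment Emergent Adverse Events". These "will be summarized using frequency counts and percentages", and in the incidence tables "a subject will be counted once if the subject reported one or more events". SAP 6.1 gives the denominator: "Percentages will be based on the number of subjects in the analysis set unless otherwise indicated". Nothing different is indicated for adverse events, so the base is the whole safety set, whatever each patient's time on drug. SAP 6.9 adds that the DPC safety analyses "will exclude any safety data that was collected after a subject had discontinued study drug", and that "No formal hypothesis testing will be conducted". Protocol 8.4.8.1 uses the same window and the same measure.

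The comparison of arms is a stated aim in SAP 2.2: "To evaluate the safety profile of octreotide capsules compared to placebo". The longest possible time at risk comes from the Protocol Synopsis: "The duration of the DPC period for each patient will be 36 weeks".

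The plan does show time on drug. Exposure in days and SRL re-initiation by time point (SAP 6.9.1.1) and time to discontinuation (SAP 6.4.1) are all reported by arm. None is linked to adverse-event incidence. The readable text of both documents plans no patient-years denominator, exposure-adjusted rate or time-to-first-event summary for adverse events.

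**The concern.** The arms may differ systematically in time on drug. Under Protocol 4.6.1, patients who meet the withdrawal criteria stop study medication and are rescued with their prior injection, and Protocol 6.10.4 prohibits parenteral SRLs during study treatment. SAP 2.1.1 hypothesizes better control on octreotide, and SAP 5.1.2 compares the proportions rescued as a secondary endpoint. If the drug works as hoped, rescue, and with it the end of the counting window, should come more often on placebo. The clearer the efficacy result, the less comparable the adverse-event percentages would be.

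Because safety is not tested, the descriptive tables are the whole safety comparison with placebo. At stake is how they are read. Octreotide could appear to cause events that merely had longer to occur, or a real excess on placebo could be hidden.

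**Working it through.** The documents state no expected adverse-event rate and no stopping rate by arm, and the power table is redacted, so there is no plan figure to reproduce. The size below is an illustration on assumed inputs.

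**Inputs from the documents:** 36-week period; window closed at last dose; each patient counted once; denominator all treated patients; about 50 patients randomized 1:1, so about 25 per arm.

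**Assumed inputs:** 36-week event risk p36 of 20% to 80%, with the same constant hazard in both arms; a fraction f of the arm stops drug at week t = 12, 16 or 20; placebo vs octreotide stopping of 30% vs 10%, 50% vs 10%, 50% vs 25% or 70% vs 25%, with 25% vs 25% as control.

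**Formulas.** Weekly hazard h = −ln(1 − p36)/36. Risk by week t: p_t = 1 − exp(−h·t). Crude percentage in an arm = (1 − f)·p36 + f·p_t. Octreotide minus placebo is therefore (f_placebo − f_octreotide)·(p36 − p_t).

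**Worked case.** p36 = 60%, t = 16: h = 0.02545 per week and p16 = 33.45%.
- Octreotide (25% stop): 0.75 × 60 + 0.25 × 33.45 = 53.4%.
- Placebo (70% stop): 0.30 × 60 + 0.70 × 33.45 = 41.4%.
- Difference 11.9 points before rounding. Mean time on drug is 36 − 0.25 × 20 = 31 weeks and 36 − 0.70 × 20 = 22 weeks.

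| 36-week risk | Stop, placebo vs octreotide | Week | Octreotide | Placebo | Difference (points) |
|---|---|---|---|---|---|
| 20% | 30% vs 10% | 20 | 19.2% | 17.5% | 1.7 (smallest) |
| 40% | 50% vs 10% | 16 | 38.0% | 30.2% | 7.9 |
| 60% | 70% vs 25% | 16 | 53.4% | 41.4% | 11.9 |
| 80% | 70% vs 25% | 12 | 70.4% | 53.1% | 17.3 (largest) |
| any | 25% vs 25% | any | equal | equal | 0 |

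The range belongs to these four pairs. Crossing their extremes widens it: 30% vs 25% at 20% risk and week 20 gives 0.05 × 8.3 = 0.4 points, and 70% vs 10% at 80% risk and week 12 gives 0.60 × 38.5 = 23.1 points.

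**Masking.** Keep the stopping of the worked case, but let the placebo hazard truly be 1.5 times higher. Placebo risk over a full 36 weeks is 1 − 0.4^1.5 = 74.7%, against 60% on octreotide. The crude table shows 54.4% vs 53.4%, so a true gap of 14.7 points appears as 1.0.

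**Time-at-risk measures.** With constant hazard, expected time to first event or last dose is (crude proportion)/h, so events divided by time return h in both arms. The rate ratio is 1.00 in every equal-hazard case. Kaplan-Meier with stopping as censoring estimates p36 in both arms.

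**Early events.** If all events fall in weeks 0 to 8 and all stops come later, the crude difference is 0. A patient-year rate then misleads. Take 40% risk in both arms, mean event time 4 weeks, and 70% vs 25% stopping at week 16:
- Octreotide: 0.4/(0.6 × 31 + 0.4 × 4) = 0.4/20.2 per week, about 103 per 100 patient-years (52-week year).
- Placebo: 0.4/(0.6 × 22 + 0.4 × 4) = 0.4/14.8 per week, about 141.
- The ratio is 0.73, although the risks are identical.

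**Scale.** With 25 per arm, the standard error of a difference at 40% or 60% is √(2 × 0.4 × 0.6/25) = 13.9 points.

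**The case against.** **Drug-type events.** A reader might infer that the gastrointestinal percentages are biased against octreotide. The documents do not support this. Protocol 7.6 reports that in the earlier Phase 3 study these events came mostly in the first two months. Rescue requires titration to four capsules a day, at least two weeks there, and biochemical plus clinical worsening at two consecutive assessments, so most rescue stops are likely to come later. This objection stands.

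**AESIs on placebo.** A reader might infer that acromegaly-symptom AESIs are broadly undercounted on placebo. Rescue under the criteria requires an exacerbation recorded as an AESI (Protocol 5.2.3), so a rescued patient already counts for any AESI. What remains is possible undercounting of further individual AESIs, of AESIs per patient, and in patients who stop for other reasons.

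**Whether placebo patients stop earlier.** Losing IGF-1 control alone does not end treatment; only the stricter combined criterion does. Symptoms may be treated while the patient stays on drug, and sites are asked to keep patients on their assigned arm. Octreotide patients may stop for severe or persistent gastrointestinal symptoms (Protocol 7.6), which would shrink or reverse the imbalance. All of this is fair. The condition is plausible, not established.

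**Size.** Larger gaps can be obtained by putting short mean exposures into 1 − exp(−H·T/36), with H events per 36 weeks. H = 1.5 with 33 vs 16 weeks gives 74.7% vs 48.7%. But a 16-week placebo mean needs 20/24 = 83% stopping at week 12, or everyone at week 16, and nothing readable in the documents supports that.

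**Already visible.** The planned exposure and discontinuation displays would reveal an imbalance, and no readable decision rule depends on these percentages. True, but those displays cannot correct an event-specific percentage.

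**Conclusion.** The point holds in conditional form. As planned, events spread over the 36 weeks are compared without regard to time at risk. If placebo patients stop earlier, identical hazards would produce crude differences of about 2 to 17 points against octreotide in the four assumed stopping patterns. The direction follows from the trial's own hypothesis; the size rests on assumed stopping fractions, stopping weeks and event risks, a constant hazard, and stopping unrelated to the event.

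The effect is on interpretation and not on an error rate. It is comparable to the sampling error at this sample size, but it is systematic and adds to that error. A supplementary display is warranted; replacing the planned tables is not.

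**What to change.** Keep the percentages and add to SAP 6.9.2.1, by arm:

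1. Kaplan-Meier estimates of time to first event with 95% CIs, censored at last blinded dose, for overall TEAEs, GI events and each AESI. If they are shown as cumulative incidence, stopping should be treated as censoring: treating it as a competing event would return the crude percentage at week 36. For AESIs, note that censoring may be informative, because symptoms contribute to rescue.
2. Exposure-adjusted incidence rates (first events per 100 patient-years at risk, 95% CI) for overall TEAEs, individual AESIs and SAEs, with a note that a single rate assumes a constant hazard and should not be used alone for early-clustered GI events.

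Visits continue to week 36 after stopping (Protocol 4.7), so off-drug events could be tabulated separately, split before and after rescue, because later events occur on injectable SRL.

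Also reconcile the TEAE window in Protocol 7.1, which runs to the end of the DPC period, with Protocol 8.4.8.1 and SAP 6.9.2.1, which end at last dose. SAP 1 says the SAP prevails, but the protocol contradicts itself.

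The cost is a few tables and one figure from onset and dosing dates already collected. At about 25 per arm the estimates will be imprecise.

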### 6.2 STUDY MEDICATION ADMINISTRATION

Study medication should be administered twice daily with a glass of water (240 mL) on an empty stomach, i.e. at least one hour prior to a meal or at least two hours after a meal.

Optional/recommended drug administration timing to patients:

Morning Dose

- Take the morning dose first thing in the morning and have breakfast at least one hour later OR
- Have breakfast and take the morning dose at least two hours later and at least one hour prior to lunch

Evening Dose

- Take the evening dose before going to bed, at least two hours after dinner or any other snack OR
- Take your evening dose at least 1 hour prior to dinner and at least two hours following an earlier snack/meal

During DPC period, study medication will be up-titrated up in all eligible patients from 1 capsule twice daily; BID (equivalent to 40 mg/day) to 2 capsules in the morning and 1 capsule in the evening/night (equivalent to 60 mg/day) to 2 capsules BID (equivalent to 80 mg/day).

The dose can be escalated any time through week 24 (including week 24); thereafter the dose must be kept stable.

The Sponsor recommends the following guiding rules for dose escalation:

- Significantly increased IGF-1 levels compared to Baseline defined as IGF-1 increase by at least 30% to  $>1 \times \text{ULN}$  (this will be flagged by the central laboratory)
- IGF-1 levels  $>1 \times \text{ULN}$  for 2 consecutive visits
- New or worsening of any one of the following acromegaly signs/symptoms: headache, fatigue, perspiration, soft tissue swelling, arthralgia, dysglycemia or hypertension or other signs that in view of the Investigator are related to acromegaly.

During the OLE period, the initial octreotide capsules dose will be 60 mg for all patients. The dose can be escalated or de-escalated upon the investigator's discretion, based on either IGF-1 and/or safety and tolerability.

The Sponsor recommends the following guiding rules for dose de-escalation:

- IGF-1 decreased by at least 50% on two consecutive visits, compared to baseline (average of 2 assessments within 2 weeks prior to randomization) and acromegaly signs/symptoms are adequately controlled (as determined by study investigator). OR

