### **Common Gastrointestinal Adverse Events**

In the previous Phase 3 Study (CH-ACM-01), GI symptoms were among the most commonly reported AEs. These AEs were generally transient and declined with time (median duration was 13 days). Most were mild to moderate in intensity, and occurred during the first two months. There was no dose relationship and most resolved with treatment continuation.

In patients who develop abdominal symptoms (e.g., nausea, vomiting, abdominal pain or diarrhea), common GI illnesses should be excluded (e.g., gastroenteritis, cholestasis, etc.), and treated accordingly. If symptoms are mild to moderate in intensity and patient is able to tolerate oral medications, consideration should be given to treating the patient symptomatically with anti-emetics or anti-diarrheals to determine if patient's GI symptoms will resolve on therapy. Patients who have severe or persistent symptoms or who cannot tolerate food/fluids should be discontinued.

Of note, a phase 1 study showed no interaction between loperamide and oral octreotide capsules.

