### 6.9.1 Study Drug Exposure and Compliance

#### 6.9.1.1 DPC period

Octreotide capsules can be up-titrated during the DPC period from 40 mg/day to 60 mg/day and 60 mg/day to 80 mg/day, based on clinical and biochemical response.

In the DPC period, the duration of study drug exposure (in days) will be summarized by the treatment group and overall, using descriptive statistics. Duration of study drug exposure will be calculated as date of last dose in the DPC period – date of first dose in the DPC period + 1.

Descriptive statistics for the time to the first dose escalation from 40 mg to 60 mg and time to the second dose escalation from 60 mg to 80 mg will also be presented by treatment group. A figure depicting the time to each dose escalation for each patient will be presented

The number and proportion of patients at each dose level (40, 60 and 80 mg/day) at the end of the DPC period, will also be presented by treatment group.

Compliance to each dose level of octreotide capsules from first dose in the DPC period through the last visit of the DPC period will be calculated and summarized by treatment group overall, and also by the final target dose level achieved within each treatment group.

For the purpose of analysis, compliance to each dose level during the DPC period will be calculated as  $100 \times (\text{total number of capsules actually taken} / \text{total number of capsules expected to be taken})$ . This calculation will be used for each dose level the patient received during the DPC period. The numbers and percentages of patients <75% compliant, 75-100% compliant, and >100% compliant will be tabulated.

The number of actual capsules taken for each dose level will be the total number of capsules dispensed – total number of capsules returned during the time the patient was on that particular dose.

The number of expected capsules taken for the target dose level will be derived as follows:

Dose Level	Expected Number of Capsules Taken
40 mg	2 capsules $\times$ (first day of the phase – last day of the phase)
60 mg	3 capsules $\times$ (first day of the phase – last day of the phase)
80 mg	4 capsules $\times$ (first day of the phase – last day of the phase)
Overall	Sum of expected number of capsules taken over all of the dose levels assigned

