#### **6.9.2.2 OLE**

AEs will be considered treatment emergent for the purpose of reporting in the OLE if they meet any of the following criteria:

- AE onset date is after the end of treatment in the DPC period (i.e., date of onset greater than the end of treatment date in the DPC period)
- AE is ongoing, and the severity worsens during the OLE (i.e., date of severity worsening is greater than the end of treatment date in the DPC period)

All summaries will be presented by final dose group (i.e., 40, 60 or 80) and overall for the OLE set.

If the day of onset of an AE is missing, then if the month and year of an onset date are on or after the date of randomization, the following rules will be applied:

- If month/year of the onset date is on or after the month/year of the end of treatment date in the DPC period, the AE will be considered treatment emergent;
- If month/year of the onset date is equal to the month/year of the end of treatment date in the DPC period, and the end date is present, the end date will be used to determine when the AE started. If the end date is on or after the end of treatment date in the DPC period, the AE will be considered treatment emergent; otherwise, if the AE stopped before randomization, then it will not be considered treatment emergent;
- If month/year of the onset date is equal to the month/year of the end of treatment date in the DPC period, and the end date is a partial date, the AE will be considered treatment emergent;
- If, despite implementing the above conventions, the onset date of the AE cannot be placed before, on, or after the end of treatment date in the DPC period, then the event will be considered treatment emergent.

Summaries of TEAEs will be presented using the MedDRA level hierarchy (system organ class, high level group term, high level term, and preferred term) as follows:

Overall (i.e., regardless of intensity or relationship to treatment)

By intensity grade (mild, moderate, severe)

By relationship to study medication (potential relationship to study treatment or unlikely/no relationship to study treatment) according to the mapping scheme below:

Related: will include all AEs with a relationship rating of “related” or “possibly related”

Not related: will include all AEs with a relationship rating of “Not related”

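### Adverse events are tabulated by final dose, so a patient's events before a dose change are counted under a dose not yet taken, and the 40/60/80 mg columns cannot be read as a dose comparison

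*SAP*

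**What the plan says.** **Attribution rule, DPC.** SAP 6.9.2.1 and Protocol 8.4.8.1 both state: "Summaries will be presented by final dose group and treatment group (i.e., octreotide 40, 60, 80, overall and placebo". Placebo is a single column.

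**Event window, DPC.** SAP 6.9.2.1 counts "All AEs that occur after randomization (i.e., date of onset is on or after the date of randomization) and on or before the end" of blinded treatment, so the whole titration phase is included.

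**Dosing, DPC.** The Protocol Synopsis says "The dose escalation will be done in a stepwise manner from 1 capsule twice daily; BID (equivalent to 40 mg/day", then 60 and 80 mg/day. Escalation is allowed up to and including Week 24 of 36. It is at the investigator's discretion and rests on IGF-1, acromegaly signs or symptoms, or both. Placebo patients undergo mock titration.

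**Attribution rule, OLE.** SAP 6.9.2.2: "All summaries will be presented by final dose group (i.e., 40, 60 or 80) and overall for the OLE set". SAP 6.9.1.2 starts every OLE patient at 60 mg/day, with movement possible in either direction.

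**What is not there.** The adverse event sections are not redacted. They contain no summary by dose at onset and no rate per patient-time by dose. SAP 6.9.1.1 does plan a summary of the "time to the first dose escalation from 40 mg to 60 mg", of the second step, and of compliance at each dose level.

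**The concern.** A column headed 80 mg invites the reader to take its contents as events that occurred on 80 mg. Under this rule it holds every event of any patient who finished on 80 mg, including events that began on 40 or 60 mg.

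Two features of the design make this more than untidy labelling.

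- **Events help to choose the column.** Protocol 6.2 lists headache, fatigue, perspiration, soft tissue swelling, arthralgia, dysglycemia and hypertension as reasons to escalate. Protocol 7.1.1 records the same list, when new or worsening, as AESIs. An AESI at 40 mg can therefore move the patient, and the event, into a higher column. In the OLE the direction can reverse: one recommended de-escalation rule includes moderate to severe GI symptoms, so a GI event at 60 mg can end up under 40 mg.
- **Events cluster early.** Of GI events in the earlier phase 3 trial, Protocol 7.6 says: "Most were mild to moderate in intensity, and occurred during the first two months". That is when patients are at or near the starting dose.

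The same section reports no dose relationship for those GI events. Final-dose columns could neither support nor contradict such a statement in this trial.

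**Working it through.** The plan states no figure on this point, so there is none to reproduce. That misattribution occurs follows from the rules alone: the window opens at randomisation, dosing begins at 40 mg/day, and events are filed under the last dose. The calculations below illustrate size and direction, and each rests on stated assumptions.

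**1. Share of an escalated patient's events that precede the final dose**

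Inputs from the documents: 36-week DPC period, escalation through Week 24. Let t be the week the final dose is reached, and assume the patient stays on treatment to Week 36.

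- Constant event rate: share = t/36. Week 4: 4/36 = 11%. Week 8: 8/36 = 22%. Week 12: 12/36 = 33%. Week 24: 24/36 = 67%.
- Early clustering: assume a fraction f of events falls evenly over Weeks 0-8 and the rest evenly over Weeks 8-36. Share = f × min(t,8)/8 + (1−f) × max(0, t−8)/28. The Protocol says most GI events came in the first two months but gives no percentage, so f is taken as 0.5 to 0.8 (assumed). Week 4: 25-40%. Week 8: 50-80%. Week 12: 57-83%. Week 24: 79-91%.

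**2. Can the final-dose columns create a trend?**

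A simulation of 200,000 patients over nine 4-week periods used the same AESI risk at every dose, constant over time. Up to Week 24, every AESI led to one dose step, as did a separate IGF-1 trigger. Making every AESI escalate is a deliberately strong assumption. With an assumed AESI risk of 10% per 4 weeks:

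| Setting | 40 mg | 60 mg | 80 mg |
|---|---|---|---|
| Patients with an AESI, by final dose; IGF-1 trigger 10% per 4 weeks | 27% | 66% | 86% |
| Patients with an AESI, by final dose; symptoms the only trigger | 27% | 100% | 100% |
| Rate by dose at onset, per 100 patient-weeks; both settings | 2.5 | 2.5 | 2.5 |

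Over AESI risks of 5-20% and IGF-1 triggers of 0 or 10%, 54-87% of the AESIs in the final-60 column and 59-90% of those in the final-80 column began at a lower dose.

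**3. Is a table by dose at onset enough by itself?**

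No, because in the DPC 40 mg always comes first. Assume 25 octreotide patients (half of about 50), of whom 8 stay at 40 mg and 17 escalate at Week 8, one event per patient on average, no dose effect, and f = 0.5 to 0.8 as above.

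- Patient-weeks at 40 mg: 8×36 + 17×8 = 424. Above 40 mg: 17×28 = 476.
- Events at 40 mg: 8 + 17f = 16.5 to 21.6. Above 40 mg: 17(1−f) = 8.5 to 3.4.
- Rate ratio, 40 mg to higher doses: (16.5/424)/(8.5/476) = 2.2, up to (21.6/424)/(3.4/476) = 7.1.

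The unsplit onset-dose rate would therefore count against 40 mg with no dose effect present. Restrict the comparison to after Week 8. The 40 mg group then has 8(1−f) = 4 to 1.6 events over 8×28 = 224 patient-weeks, and the higher doses have 8.5 to 3.4 over 476. At f = 0.5 both rates are 1.79 per 100 patient-weeks, and at f = 0.8 both are 0.71. Splitting by period removes the artefact in this example.

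**The case against.** The case against is substantial, and most of it limits the point without removing it.

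- **Stakes.** The safety objective is capsules versus placebo, the analysis is descriptive with no testing, and the overall and placebo columns sit in the same tables. Neither document sets a dose-response safety objective. About 25 octreotide patients over three columns would say little about dose under any layout. All of this stands. Still, dose is the only thing the 40/60/80 columns add to the overall column, and dose is what the rule distorts.
- **Who is affected.** A reader might infer that every patient is titrated up, because Protocol 6.2 says "study medication will be up-titrated up in all eligible patients from 1 capsule twice daily". The Synopsis and Protocol 5.2 leave escalation to the investigator, and SAP 6.9.1.1 says "Octreotide capsules can be up-titrated during the DPC period from 40 mg/day to 60 mg/day and 60 mg/day to 80 mg/day" and counts patients who end at 40 mg. The wordings should be reconciled. On the conditional reading, only patients whose dose changes are affected.
- **Early stoppers.** A reader might also count patients who stop at 40 mg because of an event as misplaced. They are not, since the event did arise at 40 mg. Their shorter exposure is simply not adjusted for, because the tables give counts and percentages.
- **Tolerability.** The DPC escalation rules rest on IGF-1 and acromegaly signs or symptoms. Safety and tolerability are a stated basis for dose changes only in the OLE.
- **Scope within the AE section.** SAP 6.9.2.1 specifies discontinuation and serious TEAEs by treatment group and relationship, without naming final dose. It does not say whether the separate AESI tables are split by dose.
- **The remedy is confounded by time.** This is the strongest objection, and it holds against an unsplit onset-dose table, as the third calculation shows. It is an argument for splitting by period, not for keeping the final-dose table as the only view.
- **Nothing is lost.** The data for an onset-dose table will exist in any case. That makes the change cheap. Specifying it before unblinding also avoids choosing the layout after seeing the events.

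**Conclusion.** The concern holds in a limited form. In both periods, the planned tables assign events that began before a dose change to a dose the patient was not yet taking, and no other planned table corrects this. The 40/60/80 mg columns should not be read as evidence for or against a dose relationship. The attribution rule itself is certain from the text.

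The size is not known, because the documents give neither a final-dose split nor escalation timing. The 22% (Week 8) and 67% (Week 24) figures assume a constant event rate and treatment to Week 36. The early-clustering and simulation figures rest on assumed rates and show direction only.

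A reader might go further and infer that the safety comparison with placebo is biased. The documents do not support that: randomised groups are compared through the overall and placebo columns, which do not depend on final dose. This is a reporting weakness worth correcting before unblinding, and it does not affect the efficacy analysis.

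**What to change.** In SAP 6.9.2.1 and 6.9.2.2, and in Protocol 8.4.8.1 to match:

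1. Add TEAE, GI-event and AESI summaries by dose at onset, with patient-time at each dose as the denominator.
2. Split them by study period, for example Weeks 0-8 and after Week 8, so that early GI events do not load onto the starting dose.
3. In the DPC, show placebo by mock capsule level (2, 3 or 4 capsules a day) as the matched control.
4. Keep the final-dose tables as supplementary, with a footnote that they do not support dose-response conclusions. The laboratory, vital sign, ECG and ultrasound summaries in SAP 6.9.3 to 6.9.6 also use final dose and could carry the same footnote.
5. Reconcile the titration wording in Protocol 6.2 with the Synopsis, Protocol 5.2 and SAP 6.9.1.1.

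**Cost.** A few extra tables and no new data. Protocol 7.1 records the date and time of each event. SAP 6.9.1.1 already derives escalation times by treatment group, and compliance per dose level in both periods requires the days spent at each dose. The cells will be small. Onset-dose rates remain non-randomised and descriptive, because dose still follows from each patient's course, and the tables should say so.
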